4.5. Analysis Window/Visit

Visit windows for each visit are defined in [Section 13.1](#). Additionally, analysis windows will be derived using below rules:

Study Visit/Study Day	Main Study	Substudy
Visit 1/Day 1	Day 1	
Visit S1/Day 8 ^a	Day 6 to Day 18	
Visit 2/Day 29	Day 19 to Day 57	
Visit 3/Day 85	Day 58 to Day 127	Day 58 to Day 115
SS Visit 4 ^b /Day 92	N/A	3 days before SS Visit 4 to 4 days after SS Visit 4

SS Visit 5 ^b /Day 99	N/A	3 days before SS Visit 5 to 7 days after SS Visit 5
SS Visit 6 ^b /Day 113	N/A	7 days before SS Visit 6 to 28 days after SS Visit 6
EOS/Day 169	Day 128 to Day 199	29 days after SS Visit 6 to Day 199

^a Safety Lead-in subject only

^b Subjects in substudy only

5. Subject Disposition

The number of subjects who were randomized and eligibility criteria met/failed will be summarized based on all enrolled subjects. Eligibility criteria met/failed will be listed based on all screened subjects.

Disposition of all enrolled subjects will be summarized by treatment groups, age groups (6 - 10 years, and 11 – 17 years, and 10 – 17 years) and overall including:

- Number screened
- Number screen failures
- Number of subjects randomized
- Number of subjects randomized, not vaccinated
- Number of subjects vaccinated
- Safety Analysis Set
- ITT Analysis Set
- Immunogenicity Analysis Set
- Per Protocol Immunogenicity Analysis Set
- Safety Lead-in Analysis Set
- Number of subjects who participated in substudy
- Number of subjects who completed substudy
- Number of subjects who completed study (EOS Visit)
- Number of subjects who prematurely discontinued study
- Primary reason for premature discontinuation of study

Primary reasons for study discontinuation collected on the Study Termination eCRF will be summarized with the following categories:

- Adverse Event

- Lost to Follow-Up
- Withdrawal of Consent
- Investigator Decision
- Sponsor Decision
- Death
- Other

A by subject listing will be provided based on the ITT Analysis set, subjects who are willing to participate in the substudy will also be included.

Disposition of all subjects who participate in substudy will be summarized by treatment groups, age groups (6 - 10 years, and 11 – 17 years) and overall including:

- Number of subjects who participated in substudy
- Number of subjects vaccinated on Day 1
- Number of subjects vaccinated on Day 85
- Number of subjects who are also in the following analysis sets:
 - Safety Analysis Set
 - Immunogenicity Analysis Set
 - Per Protocol Immunogenicity Analysis Set
- Number of subjects who prematurely discontinued study
- Primary reasons for premature discontinuation of study

Primary reasons for study discontinuation for subjects who are willing to participate in substudy include:

- Adverse Event
- Lost to Follow-Up
- Withdrawal of Consent
- Investigator Decision
- Sponsor Decision
- Death
- Other

5.1.Protocol Deviations

A deviation from the protocol is an unintended or unanticipated departure from the agreed procedures or processes. A significant deviation occurs when there is nonadherence to the protocol or to local regulations or ICH GCP guidelines that may or may not result in a significant, additional risk to the participant or impacts the integrity of study data. Deviations

will be assessed with Sponsor involvement and deemed significant or non-significant prior to database lock.

Protocol deviations will be documented by the clinical monitor throughout the course of monitoring visits. Any overdose should be recorded as a protocol deviation. For subjects who are designated to provide mid-turbinate/nasopharyngeal samples on Day 29, it will not be considered a protocol deviation if subjects provide samples on Day 85 instead. Significant protocol deviations will be summarized using the ITT Analysis Set.

A by-subject listing will be provided based on the ITT Analysis Set including both the significant and non-significant protocol deviations. A separate listing will be provided to list the reasons subjects were excluded for the Per-Protocol Immunogenicity Analysis Set based on Immunogenicity Analysis Set.

6. Demographics and Baseline Characteristics

6.1. Demographics

Demographic and baseline characteristics data to be analyzed will include age, sex, race, ethnicity, weight, height, and body mass index (BMI) on the ITT Analysis set and PP Immunogenicity Analysis set by treatment group and overall, and by age group (6 - 10 years, and 11 – 17 years, and 10 – 17 years). Z-scores of height, weight, and BMI will be calculated using a SAS macro and the reference data file from the CDC website (<https://www.cdc.gov/nccdphp/dnpao/growthcharts/resources/sas.htm>)

The following characteristics will be summarized as continuous variables:

- Age (years)
- Weight (kg)
- Weight Z-score
- Height (cm)
- Height Z-score
- BMI (kg/m^2)
- BMI Z-score
- Time since last aP vaccination

Time since last aP vaccination prior to study entry will be derived based on the country's immunization schedule. The schedule is as below:

- 1) UK – 3 years old
- 2) Australia – 4 years old and 12-13 years old
- 3) Costa Rica – 4 years old

The estimated time since last aP vaccination derive method is:

- 1) UK site: estimated time since last aPV = Age -3
- 2) Costa Rica site: estimated time since last aPV = Age -4

- 3) Australia if age is ≤ 12 : estimated time since last aPV = Age -4
- 4) Australia if age is > 12 : estimated time since last aPV = Age -12

The following characteristics will be summarized as categorical variables:

- Sex (Male, Female)
- Age group (6 - 10 years, and 11 – 17 years, and 10 – 17 years)
- Race (White, Black, Asian, Pacific Islander, Aboriginal or Torres Strait Islander, Mixed or Multiple ethnic groups, Other)
- Ethnicity (Hispanic, non-Hispanic, Not reported, Unknown)
- County

A by-subject listing will be provided based on the ITT Analysis set.

6.2.Medical History

A medical history, including vaccination history, prior and concomitant medical conditions, and surgeries/significant procedures for medical conditions (eg, endoscopy, tonsillectomy), will be collected at screening and reviewed and/or updated on Day 1 if screening occurs prior to Day 1.

Medical history will be summarized based on the ITT Analysis Set and will be coded according to the latest version of Medical Drug Regulatory Activities (MedDRA). Medical history will be summarized by system organ class (SOC) and preferred term (PT), with SOCs sorted alphabetically and PTs within each SOC in descending order of frequency.

A by-subject listing will be provided for medical history based on the ITT Analysis set.

7. Treatments and Medications

7.1.Prior and Concomitant Medications

The Anatomical Therapeutic Chemical (ATC) coding scheme of the latest World Health Organization Drug Dictionary (WHODrug) will be used to group medications into relevant categories.

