4.1.2 Exclusion Criteria

Subjects meeting any of the following criteria (by review of medical history and subject intake) will be excluded from the study:

1. The subject has a history of pertussis-containing vaccination (inclusive of school vaccination programs) or documented *B. pertussis* infection within 3 years prior to Day 1 and/or a history of Td-containing vaccination (without pertussis vaccine component) within 1 month prior to Day 1.

2. The subject has a chronic significant illness actively being treated or a history of recent intervention for worsening or fluctuating symptoms (at the discretion of the investigator).
3. The subject has a history of cancer (malignancy).
4. The subject has a congenital, hereditary, or acquired disease or disorder classified as autoimmune, immunodeficient, coagulopathy, hepatic, renal, neurologic (including a history of Bell's palsy), or moderate to severe cognitive. (Attention deficit hyperactivity disorder permitted.)
5. The subject currently uses smoking products (including vaping and e-cigarettes) and is unwilling to refrain from use from Day 1 through Day 29 following any study vaccination.
6. The subject has received immunoglobulin, blood-derived products, systemic corticosteroids (at a dose of >10 mg per day for more than 10 days), or other immunosuppressant drugs within 90 days prior to Day 1.
7. The subject has any chronic pulmonary disease requiring active medication or pulmonary therapies, with the following exceptions:
 - a) Subjects with exercise-induced bronchospasm, if currently well controlled, who are willing to refrain from intense exercise for 7 days following study vaccination or
 - b) Subjects with Step 1 (intermittent) asthma classification who have not had an exacerbation requiring oral systemic corticosteroids in the past year; have an FEV1 documented to be >80%; do not have restrictions in normal activity due to breathing issues; and have used a short-acting beta-agonist less than or equal to 2 days per week over the past 2 months.

NOTE: Subjects in the safety lead-in cohort are not allowed to have these exceptions.

8. The subject has a history of oro/nasopharynx surgery (eg, adenoidectomy, tonsillectomy) within 60 days prior to Day 1.
9. The subject has a known hypersensitivity to latex or any component of any study vaccine. Specific to Boostrix: the subject has known hypersensitivity to neomycin or

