6.2 Medical History

A medical history (including vaccination history, prior and concomitant medical conditions, and surgeries/significant procedures for medical conditions [eg, endoscopy, tonsillectomy]) will be collected at screening and reviewed and/or updated on Day 1 if screening occurs prior to Day 1.

Ideally, the subject will provide a vaccination card (or equivalent) or the subject's vaccination history can be accessed via a centralized vaccination register to record last known pertussis vaccination. If the subject's vaccination history is not available, the timing of prior pertussis vaccine may be estimated based on the national vaccination schedule appropriate for the age of subject.

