2.2.3. Mucosal Secretory Immunogenicity (S-IgA)

- To demonstrate BPZE1 induction of mucosal S-IgA immunity is non-inferior to Boostrix at Day 29 as measured by antibodies to WCE (BPZE1 vs Boostrix).
- To demonstrate BPZE1 induction of mucosal S-IgA immunity is greater than baseline at Day 29 (BPZE1, BPZE1 + Boostrix).
- To demonstrate BPZE1 induction of mucosal S-IgA immunity remains greater than baseline over the study period and at Day 169/end of study (EOS) (BPZE1, BPZE1 + Boostrix).
- To demonstrate BPZE1 + Boostrix induction of mucosal S-IgA immunity is non-inferior to BPZE1 at Days 29 and 169/EOS (BPZE1 + Boostrix vs BPZE1).
- To assess if age, time since last aP vaccination (prior to study entry), or other baseline demographics have a differential response to induction of mucosal S-IgA immunity (BPZE1, BPZE1 + Boostrix) at Day 29.
- To assess if baseline antibody values, by baseline quantile, have variable responses at Day 29 to induction of S-IgA immunity when BPZE1 is given alone or with Boostrix (BPZE1, BPZE1 + Boostrix).
- To assess seroconversion for each of the anti-pertussis S-IgA antibodies at Day 29 (BPZE1, BPZE1 + Boostrix, Boostrix). Additional combinations of antibody response (WCE, PT, FHA, PRN, other) may also be tested.
- To assess reverse cumulative distribution curves for S-IgA at Day 29.

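### Time since the last aP dose is computed from national schedules for every subject, bypassing recorded vaccination history and producing values under 3 years that exclusion 1 rules out

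*SAP*

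**What the plan says.** SAP section 6.1 states: "Time since last aP vaccination prior to study entry will be derived based on the country's immunization schedule". The schedule it lists for Australia is "Australia – 4 years old and 12-13 years old"; the UK and Costa Rica have one dose each, at 3 and 4 years. The formulas are "UK site: estimated time since last aPV = Age -3", "Costa Rica site: estimated time since last aPV = Age -4", age minus 4 for Australians up to 12, and "Australia if age is > 12 : estimated time since last aPV = Age -12". No step uses a recorded date.

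Protocol section 6.2 works the other way round. It begins "Ideally, the subject will provide a vaccination card (or equivalent", or a central register may be consulted, so that the last known pertussis vaccination is recorded. Only when the history is unavailable may its timing be estimated from the national schedule. SAP section 1 says the SAP governs where the two differ on planned analyses.

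Exclusion 1 (Protocol 4.1.2) starts "The subject has a history of pertussis-containing vaccination (inclusive of school vaccination programs" and sets the limit at 3 years before Day 1.

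The variable is summarised at baseline (SAP 6.1). It is split at its median for the Day 29 S-IgA and serum subgroup analyses (SAP 8.3.1, 8.3.2). It is also named in secondary objectives such as "To assess if age, time since last aP vaccination (prior to study entry), or other baseline demographics have a differential response" (SAP 2.2.3; SAP 2.2.4 has the serum counterpart).

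**The concern.** A fallback for missing history has become the rule for everyone, and it conflicts with eligibility. The Australian rule assumes that each subject over 12 had the adolescent dose at 12. An eligible 13- or 14-year-old cannot have had that dose, because it would lie within 3 years of Day 1. The subjects coded as most recently vaccinated may therefore be among those vaccinated longest ago.

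Two outputs are at stake. The baseline table could show minimum intervals of 1 or 2 years, which a reader would take for eligibility violations. The median split would mix long-interval adolescents into the short-interval half, blurring the contrast it is meant to show. In addition, age minus a constant carries no information beyond age within a country that has a single constant.

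**Working it through.** The plan gives no figure to reproduce here, so the check applies its formulas to every eligible age.

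**Inputs.** Ages 6 to 17 (Protocol 4.1.1); 3-year limit (Protocol 4.1.2, exclusion 1); formulas from SAP 6.1.

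**Step 1: derived years since last aP dose, at selected ages in whole years.**

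| Age | UK (age − 3) | Costa Rica (age − 4) | Australia (age − 4; age − 12 above 12) |
|---|---|---|---|
| 6 | 3 | 2 | 2 |
| 7 | 4 | 3 | 3 |
| 12 | 9 | 8 | 8 |
| 13 | 10 | 9 | 1 |
| 14 | 11 | 10 | 2 |
| 15 | 12 | 11 | 3 |
| 17 | 14 | 13 | 5 |

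The values below 3 are Australia at 6, 13 and 14, and Costa Rica at 6. The SAP does not say whether age is in whole or decimal years. With decimal age, every Australian above 12.00 and below 15.00 gets less than 3.

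**Step 2: size of the error.** If the last dose was the age-4 one, the interval is 13 − 4 = 9 or 14 − 4 = 10 years. The error is 9 − 1 = 8 or 10 − 2 = 8 years. Whatever the true date, eligibility requires at least 3 years, so the error is at least 3 − 1 = 2 years at age 13 and 3 − 2 = 1 year at age 14. For the 6-year-olds coded 2, it is at least 3 − 2 = 1 year.

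**Step 3: can this change the subgroup?** The documents do not give the median. Assuming ages uniform over 6 to 17, the median derived value is 4 in Australia alone, 7.5 in Costa Rica alone and 8.5 in the UK alone. Any country mix therefore lies between 4 and 8.5. Under that assumption, a subject coded 1 or 2 instead of 9 or 10 moves from the upper half to the lower.

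**Step 4: relation to age.** In the UK and in Costa Rica the correlation with age is exactly 1, and the columns intercept, age and time have rank 2 of 3. In Australia it is about 0.04, but only because of the 8-year drop between ages 12 and 13. Pooled over countries with uniform ages, it depends on the assumed mix: 0.99 (UK and Costa Rica equally), 0.65 (equal thirds), 0.43 (60% Australia, 20% each of the others). The separation comes from country and from the Australian step.

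**Step 5: would recorded dates remove this?** Suppose the actual age at the last dose scatters around the scheduled age with standard deviation s, independently of current age. Then r = SD(age) / √(SD(age)² + s²), with SD(age) about 3.45. For s = 0.25, 0.5 and 1.0 years, r is about 0.997, 0.99 and 0.96. Recorded dates correct wrong values but would barely separate the interval from age in a country with one scheduled booster.

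**The case against.** The strongest reply is that the reach is narrow. The variable feeds one baseline row and secondary subgroup displays. The primary paired t-test (SAP 8.1) and the key secondary IgG comparisons (SAP 8.2) do not use it. That stands.

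The protocol also describes obtaining a card or register entry as the ideal, so complete dates cannot be assumed, and the documents give no completeness figure. That stands too. It supports keeping a fallback, but not ignoring the records that exist. An Australian 13- or 14-year-old without a record should be uncommon as well, because the protocol's own schedule estimate could point to a dose inside the 3-year limit and hence to exclusion.

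Four stronger readings are tempting, and the documents do not support them:

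- A reader might infer that a derived value under 3 years removes a subject from the Immunogenicity Analysis Set. SAP 4.3.3 turns on whether a pertussis vaccine was actually received, and nothing links membership to this estimate.
- A reader might infer that the secondary objective cannot be answered. The SAP implements it as subgroup summaries, one factor at a time. The S-IgA ANCOVA in SAP 8.3.1 contains age and baseline antibody but not time since aP. Although SAP 3.2.2.3 mentions a covariate analysis, no specified model holds both age and time, so none is rank-deficient. The fair criticism is confounded interpretation.
- A reader might infer that the affected adolescents certainly change subgroup. That depends on the actual median, which is not given.
- A reader might infer that recorded dates would make the interval's effect separable from age. Step 5 shows that they largely would not.

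**Conclusion.** The point holds, with limited reach. SAP 6.1 departs from Protocol 6.2 by not using recorded vaccination history, and its formulas return intervals that exclusion 1 rules out: 1 and 2 years for Australians aged 13 and 14, and 2 years for Australian 6-year-olds. The same holds for 6-year-olds in Costa Rica if the Costa Rica-only protocol version of 10 October 2023, which is not among the documents, keeps exclusion 1. The error is 8 years where the last dose was the one at age 4, and at least 1 to 2 years in any eligible 13- or 14-year-old.

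Wrong values will reach the baseline table if such subjects are enrolled, and subjects can land in the wrong half of the median split. The number affected is unknown because the documents give neither the country mix nor the age distribution. The study's success criterion is untouched. The collinearity with age is a caveat on interpretation: exact within the UK and Costa Rica when schedule-derived, and likely still strong with recorded dates.

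**What to change.** In SAP 6.1:

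1. Derive the interval as Day 1 minus the recorded date of the last pertussis vaccination wherever one exists.
2. Use the national schedule only when there is no record, and flag the value as estimated.
3. Do not let an estimate fall below the 3-year eligibility limit. For Australians over 12 whose age-minus-12 value is under 3 years, use the age-4 dose. For 6-year-olds whose age-minus-4 value is under 3 years, set the value to missing or to the 3-year bound, and flag it.
4. State whether age is in whole or decimal years.

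In SAP 8.3.1 and 8.3.2, repeat the time-since-aP subgroup analysis in subjects with recorded dates, and report how many values were recorded and how many estimated. Add the caveat that the variable is an exact function of age within the UK and Costa Rica when schedule-derived, probably stays strongly correlated with age otherwise, and should not be interpreted as a separate effect. Record the change in SAP section 11.

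The cost is SAP wording, one derivation and a repeated subgroup display. Design, sample size and formal tests do not change. How complete the recorded dates are must be checked in the database first.

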7.1.1. Prior Medications

Prior medications are defined as non-study medications with a start date before the date of vaccination. Prior medications that continue on and after the date of vaccination will be reported as both prior and concomitant medications. Prior medications will be summarized based on the ITT Analysis Set by ATC2 level and preferred medication names, with ATC2 level sorted alphabetically and preferred names within each ATC2 level in descending order of frequency.

A by-subject listing will be provided for prior medications based on the ITT Analysis Set.

7.1.2. Concomitant Medications

Concomitant medications are defined as all medications and over the counter (OTC) products, including herbal supplements and multivitamins, taken by the subject from the time of signing the ICF through Day 29 and from Day 85 (following study vaccination) through Day 113 for

subjects participating in the optional substudy, or through an early termination visit, if prior to these time points. The use of anti-pyrogenic medication will be specifically queried by diary during the 7 days following any study vaccination. Concomitant medications associated with any MAAE will be recorded through 84 days following any study vaccination. Concomitant medications associated with any AESI or SAE will be recorded through Day 169/EOS.

Concomitant medications will be summarized by ATC2 level and standardized medication names, with ATC2 level sorted alphabetically and standardized names within each ATC2 level in descending order of frequency. Summaries will be provided based on the Safety Analysis Set.

A by-subject listing will be provided for concomitant medications based on the Safety Analysis set.

7.1.3. Concomitant Vaccination

Vaccines received outside of the study will be specifically queried during each visit and recorded through Day 169/EOS. Concomitant vaccinations will be summarized based on the Safety Analysis Set.

A by-subject listing will be provided for concomitant vaccinations based on the Safety Analysis set.

7.2. Study Treatments

7.2.1. Treatment Compliance and Modifications

A by-subject listing will be provided based on the ITT Analysis Set, and subjects in the optional substudy will also be included.

8. Immunogenicity Analysis

Immunogenicity Analyses will be performed based on Per Protocol Immunogenicity Analysis Set, and sensitivity analyses will be performed where specified.

8.1. Analyses of Primary Endpoints

The estimand description for the primary endpoint analysis is provided in the following table.

Estimand attributes for the primary endpoint analysis	
Estimand Label	Estimand
Estimand Description	GMFR (from baseline) of BPZE1 induction of mucosal S-IgA against WCE at Day 29 following vaccination at Day 1 in the BPZE1 treatment group (BPZE1 is administered intranasally via a MAD) and BPZE1+Boostrix treatment group (BPZE1 is administered intranasally via a MAD and Boostrix is administrated by IM injection).
Target population	All School-Age Children subjects in the Per Protocol Immunogenicity Analysis Set
Treatment Condition	Treatment group A: BPZE1 (2 x 0.4 mL (0.4 mL per nostril containing half the dose (5×10^8 CFU) to give a total dose of 10^9 CFU) administered intranasally via a MAD) on Day 1; and an IM injection of 0.5 mL placebo (sterile normal saline for injection, or similar sponsor-approved substitute) to the deltoid region on Day 1. Treatment group B: BPZE1 (2 x 0.4 mL (0.4 mL per nostril containing half the dose (5×10^8 CFU) to give a total dose of 10^9 CFU) administered intranasally via a MAD) on Day 1; and an IM injection of 0.5 mL Boostrix (includes aP vaccine, manufactured by GlaxoSmithKline) to the deltoid region on Day 1.
Endpoint	GMFR of BPZE1 induction of mucosal S-IgA against WCE at Day 29 by treatment group [BPZE1 (Treatment group A), BPZE1 + Boostrix (Treatment group B)]. Mucosal S-IgA will be normalized as [specific S-IgA]/[Total S-IgA (mg/mL)].
Population-level summary	GMFR (from baseline) at Day 29 in each BPZE1 and BPZE1+Boostrix treatment groups.
Intercurrent Events and Strategies	None.

For mucosal S-IgA against WCE at Day 29, GMFR will be summarized for all treatment groups using descriptive statistics, and the 2-sided 95% CI for change from baseline in GMFR will be calculated. A superiority hypothesis will be tested to demonstrate BPZE1 can adequately induce mucosal S-IgA against WCE at Day 29 by GMFR.

The formal superiority hypothesis is:

$$H_0: GMFR \leq 1 \text{ vs. } H_A: GMFR > 1$$

The GMFR is defined as the ratio of GMT at Day 29 and GMT at baseline, i.e., $GMFR = \left(\frac{\mu_{D29}}{\mu_{BL}} \right)$, with μ_{D29} and μ_{BL} being the GMTs at Day 29 and baseline, respectively.

After natural logarithmic transformation, $\ln(GMFR) = \ln(\mu_{D29}) - \ln(\mu_{BL})$. Therefore, the hypotheses can be expressed on the natural log scale as:

$$H_0: \ln(\mu_{D29}) - \ln(\mu_{BL}) \leq 0 \text{ vs. } H_A: \ln(\mu_{D29}) - \ln(\mu_{BL}) > 0$$

After natural logarithmic transformation, a paired *t*-test will be used to test the difference of mucosal S-IgA against WCE at Day 29 compared with baseline. The superiority objective will be demonstrated if the lower limit of the 95% CI for the difference of mucosal S-IgA against WCE at Day 29 compared to baseline on the natural log scale is greater than 0. The superiority hypothesis will be tested in treatment groups BPZE1 and BPZE1 + Boostrix separately. These 2 primary comparisons will be tested at a one-sided significance level of 0.025. The study is considered a success if both primary comparisons meet statistical significance.

Sensitivity analysis for primary endpoints will be performed based on the Immunogenicity Analysis Set.

